4.2 Schedule of Events

The schedule for study activities is presented in [Table 2](#).

Confidential

Table 2 Schedule of Events – Screening and Treatment Periods

Procedure	Study Visit Type / Day			
	Screening	Study Drug Treatment	Diary Completion/ Telephone Contact	Telephone Contact
	Study Center Visit		Remote Visit	
	Day 1 Pre-Dose	Day 1	Daily Days 1 to 14	Days 21 and 28 ±2 days
Informed consent	X			
Eligibility criteria check	X			
Demographics	X			
Medical history	X			
Focused cardiovascular and respiratory physical examination	X			
Height and weight	X			
Blood pressure and respiratory rate	X			
Urine pregnancy test ^a	X			
Randomization	X			
Study drug administration ^b		X		
Resting SpO ₂ ^c	X		X ^d	
Resting pulse rate ^c	X		X ^d	
Oral temperature ^c	X		X ^d	
Baseline/Concomitant medications	X		X	X
AEs			X	X
eDiary completion for COVID-19 symptoms ^e	X		X	
Criteria for the Assessment of Severity of Illness in Patients with COVID-19 ^f	X			X
Daily telephone contact to document concomitant medications, clinical and hospitalization status and AEs ^g			X	
Follow-up contact for hospitalization status, COVID-19 outcomes, and AEs ^h				X

^a For women of child-bearing potential only. Results must be available and confirmed to be negative before study drug administration.

^b Study drug is to be administered with the patient in the supine position. The patient is to remain in the supine position for 30 minutes thereafter and be observed for at least 2 hours post intranasal administration.

^c To be measured remotely daily at 09:00 and 16:00 hours or at any time the patient experiences worsening symptoms using the study-supplied devices and recorded in the eDiary. Resting SpO₂ and pulse are to be measured at rest for 2 minutes. A ±1 hour window will be allowed. On Day 1, only the afternoon (16:00 hours) measurement is required and may be measured at the study center or remotely.

^d If the Screening visit occurs in the morning, the patient will be responsible for recording the 16:00 measurements at home later that day; if the visit occurs after 16:00, measurements will commence at home the following morning.

Confidential

- ^e The following symptoms will be recorded: fatigue, chills, headache, cough (with or without sputum production), myalgia, sore throat, shortness of breath, nasal congestion, diarrhea, and nausea or vomiting.
 - ^f After Screening, the patient will be assessed at different timepoints over the course of the trial. The final determination will be made on Day 28 in patients who are not hospitalized and Day 42 in patients who are hospitalized.
 - ^g Telephone calls to the patient will commence on Day 2. The script for these calls is provided in Appendix A of the Protocol.
 - ^h The script for the Day 21 and Day 28 phone calls is provided in Appendix B of the Protocol. For hospitalized patients, the dates and times of hospital admission/discharge, date and time of intensive care unit admission/discharge, and ventilation requirement are to be recorded, as applicable. Patients who remain hospitalized at the end of 28 days will be followed through Day 42 or death, whichever is sooner.
-

4.3 Study Population

Approximately 96 ambulatory patients with COVID-19, with onset of fever, cough, or shortness of breath within 48 hours and a confirmation of SARS-CoV-2 infection by a polymerase chain reaction (PCR)-based diagnostic within the prior 24 hours, will be enrolled at up to 5 study centers in the US.

The Inclusion and Exclusion Criteria of patients are provided in Protocol Sections 5.2 and 5.3, respectively.

4.4 Randomization and Treatment Assignments

Following completion of the Screening activities, patients who meet all the inclusion and none of the exclusion criteria will be registered by the Interactive Web Response System (IWRS). Eligible patients will be randomly assigned in a 1:1 ratio to the NasoVAX or placebo group within each cohort. Randomization will proceed in 3 cohorts defined by age and risk factors (Exclusion Criterion 5 in the Protocol) for severe COVID-19. The cohorts will be enrolled in ascending order, with Cohort 1 preceding Cohort 2, and Cohort 2 preceding Cohort 3. Cohort 2 will be stratified by age groups of 35-64 years and 65 years and above, whereas Cohort 3 will be stratified by age groups (ages 35-64 years, ages 65 and above) and co-morbidity (one or more risk factors present, no risk factors present). Patients in Cohorts 2 and 3 will be stratified first, and then randomized 1:1 to NasoVAX or placebo. Enrollment of patients ages 35-49 will not exceed approximate 30% of the randomized population of either treatment arm.

The randomization list will be generated by an independent unblinded statistician.

4.5 Dose and Administration

NasoVAX or normal saline placebo will be administered as a single intranasal dose of 0.5 mL (0.25 mL in each nostril) on Day 1 in the supine position followed by remaining in supine position for 30 minutes, according to the patient's treatment assignment. Patients will be observed for at least 2 hours post intranasal administration.

4.6 Blinding and Unblinding

The Pharmacy staff will be unblinded for the purpose of final drug preparation. The pharmacist will consult the unblinded study statistician for dose allocation and the Pharmacy staff will prepare each dose in compliance with the randomization list.

Since formulations cannot be made to look identical, a blinded syringe will be used for administration. Study staff either preparing the syringes and/or administering the study drug will be independent and will not take part in any other activity of the study (eg, telephone contact).

Knowledge of the randomization list will be limited to the persons responsible for creation of the randomization list, pharmacy staff who prepare the study drugs, and any unblinded study monitors or auditors, until all data collection and verification activities and assignment of

patients to the analysis populations has been completed, the database has been locked, and the study formally unblinded.

Data provided to the DMC may be unblinded, as required, for the assessment of safety.

If unblinding is required in the interest of the safety of a patient, an Investigator will discuss the matter with the Sponsor before unblinding. In a medical emergency, the Investigator or delegate may unblind via the IWRS for that patient without prior consultation with the Sponsor. In that event, the Investigator or delegate will notify the Sponsor as soon as possible that the randomization code has been broken for the patient. If the blind is broken, the date, time, and reason must be recorded.

Patients may also be unblinded for the assessment of Stopping Rules, DMC evaluations, expedited safety reports, and the emergency unblinding of individual patients, as detailed in a separate Safety Management Plan.

4.7 Prior and Concomitant Therapy

In the interests of patient safety and acceptable standards of medical care, both the Investigator and patient personal physician(s) will be permitted to prescribe additional treatment(s) at his/her discretion.

Any medications that are ongoing at Screening are to be documented in the electronic case report form (eCRF). Thereafter, all concomitant medications, including supplemental oxygen, through 30 days after study drug administration are to be documented in the eCRF.

Concomitant medications, including supplemental oxygen, are to be recorded in the source documents and in the eCRF.

4.7.1 Prohibited Prior and Concomitant Medications

Prohibited prior and concomitant medications are as follows:

- Hydroxychloroquine within 4 months or chloroquine within 9 months of Screening
 - Any treatment known to affect the immune system, including but not limited to oral or intravenous corticosteroids, alkylating drugs, antimetabolites, cytotoxic drugs, radiation, immune-modulating biologics, within 30 days of Screening
 - Live vaccines (such as live influenza vaccinations or live travel vaccinations) within 30 days of Screening and through Day 14 post study drug administration
 - Receipt of any investigational drug or treatment within 30 days of Screening.
 - The above medications are prohibited through Day 14 or hospitalization, and all other concomitant medications are permitted. If a patient is hospitalized due to COVID-19, there
-

are no restrictions regarding concomitant medications. However, all medications administered, including antipyretics, bronchodilators, and supplemental oxygen requirements, are to be documented in the eCRF.

5 PREMATURE DISCONTINUATION

5.1.1 Individual Patients

Patients can choose to discontinue study participation at any time, for any reason, without prejudice to their future medical care. Patients could be discontinued for any of the following reasons:

- Patient request/withdrawal of consent
- Noncompliance with study requirements
- Loss to follow-up
- Investigator discretion
- Sponsor request, including termination of the study by the Sponsor

For all patients who discontinue for reasons other than withdrawal of consent, a final telephone contact will be made by study center personnel to document final outcome and AEs. Serious adverse event (SAEs), hospital, and ICU lengths of stays, and mortality in hospitalized patients also will be documented.

Eligible patients who are randomized and withdrawn before study drug administration will be replaced. Patients who receive study drug who are subsequently withdrawn from the study will not be replaced.

To optimize the safety of study participants, once patients receive study drug, all efforts will be made to monitor their clinical courses according to study procedures.

5.1.2 Stopping Rules

Enrollment and study drug treatment will be temporarily halted pending DMC review for any of the following reasons:

- Any SAE considered possibly or probably related to study drug
 - Any Grade 4 or Grade 5 (death) AE considered possibly or probably related to study drug
 - Three or more patients in the same cohort experience the same Grade 3 AE in the same Medical Dictionary for Regulatory Activities (MedDRA) System Organ Class considered possibly or probably related to study drug
-

Confidential

- Hospitalization rates in either treatment group in individual cohorts exceeding:
 - 15% (Cohort 1 only)
 - 20% (Cohort 2 only)
 - 25% (Cohort 3 only)
- Mechanical ventilation rates in either treatment group in individual cohorts equal to or exceeding:
 - 2 patients (Cohort 1 only)
 - 3 patients (Cohort 2 only)
 - 4 patients (Cohort 3 only)

The DMC will be advised each time a patient dies or is hospitalized. The DMC may unblind individual patients for the assessment of the relationship of the event to study drug. The DMC may recommend resumption of dosing if patient safety is not considered to be at significant risk following analysis.

5.1.3 Study as a Whole

Both the Sponsor and the Investigator reserve the right to terminate the study at the Investigator's site at any time. Should this be necessary, the Sponsor or a specified designee will inform the appropriate regulatory authorities of the termination of the study and the reasons for its termination, and the Investigator will inform the IRB of the same. In terminating the study, the Sponsor and the Investigator will assure that adequate consideration is given to the protection of the patients' interests.

Possible reasons for termination are:

- Safety reasons –the incidence of AEs in this or any other study using the same investigational product(s) indicates a potential health risk for the patients
 - New scientific knowledge becomes known that makes the objectives of the study no longer feasible/valid
 - Unsatisfactory enrollment of patients
-

6 DESCRIPTION OF STUDY PROCEDURES

Patients will be solicited from medical office, clinics, or hospitals where they seek care for COVID-19 symptoms and where COVID-19 test positivity is documented. All recruitment materials will be reviewed by the Institutional Review Board overseeing the study. Patients need not have a personal doctor to participate in the study. Patients themselves must provide written informed consent before the performance of any study-related procedures, and surrogate consent by family members, designated legal representatives, or caregivers will not be permitted. In the event that the patient progresses to hospitalization or is unable to complete the eDiary or telephone calls, designated legal representatives, family members or caregivers will be contacted, as provided by informed consent, for this information.

6.1 Screening Assessments

6.1.1 *Demographics*

Demographic data (age, sex, race, ethnicity) will be recorded during Screening. The name and contact information for the patient's family member(s) or caregiver(s) will also be obtained in the event that the eDiary (Section 6.2.2) is not completed patient does not respond to telephone calls (Section 6.2.3). The contact information for the patient's personal doctor (s) will also be obtained.

6.1.2 *Medical History*

A complete medical history, including diabetes, hypertension, and respiratory history, is to be documented during Screening. Smoking history of use of any inhalation products (eg, nicotine-containing products including e-cigarettes or e-vaporizers) is to be documented.

The patient's COVID-19 symptom history, including fever (temperature >100.4°F [38.0°C]), fatigue, chills, headache, cough (with or without sputum production), myalgia, sore throat, shortness of breath, nasal congestion, diarrhea, and nausea or vomiting is to be documented, including date of onset of symptoms, and any laboratory or radiological test results obtained.

The date of initial SARS-CoV-2 positivity also is to be documented.

6.1.3 *Pregnancy Testing (Females of Childbearing Potential Only)*

A urine pregnancy test is to be performed for female patients of childbearing potential at Screening. Results must be available and confirmed to be negative before study drug administration.

6.1.4 *Concomitant Medications*

Concomitant medications will be documented as described in Protocol Section 6.7.

6.2 Efficacy Assessments

6.2.1 *Pulse Oximetry, Pulse Rate, and Temperature*

After signing informed consent, patients will be provided with a fingertip pulse oximetry device that connects to a mobile device connecting to a tablet that will be supplied to the patient to measure resting SpO₂ and resting pulse rate. Patients will be trained on the use of the device and tablet. This device will be used to determine study eligibility at Screening, and if the patient is eligible, he/she will return home with the device for remote monitoring of resting SpO₂ and resting pulse rate for the duration of the study.

6.2.1.1 *Screening*

Resting SpO₂ and resting pulse rate will be measured twice at Screening, with each measurement being of 2 minutes duration. For the first measurement, the patient will be sitting and breathing room air for at least 5 minutes before the measurement is made. A 3- to 5-minute interval will transpire before the second measurement is commenced. The patient should continue to sit and breath room air through the time that the second measurement is completed. To ensure stabilization of resting SpO₂, only the average of resting SpO₂ in the second minute of each measurement will be used to determine study eligibility. Resting pulse rate will also be determined during this time. To be eligible for the study, patients will be required to have an average resting SpO₂ $\geq 96.0\%$ on both measurements. Average resting pulse rate will also be determined from these measurements. Oral temperature will also be recorded.

6.2.1.2 *Home Monitoring*

Resting SpO₂ and resting pulse rate will be measured remotely twice daily at 09:00 hours and 16:00 hours for 14 days, with each measurement being of 2 minutes duration and with a 1-hour window around each time point. They will also record resting SpO₂ and resting pulse rate at any time they experience worsening symptoms. The patient will be sitting at rest and breathing room air for at least 5 minutes before these measurements are made and should continue to sit and breath room air through the time that the measurement is completed. To ensure stabilization of resting SpO₂ and resting pulse measurements, only the averages of these parameters in the second minute of measurement will be analyzed.

Similarly, patients will be provided with a digital thermometer to measure oral temperature at 09:00 hours and 16:00 hours twice daily, with a 1-hour window around each time point, and at any time they experience worsening symptoms through Day 14, with results recorded in the eDiary.

Resting SpO₂ and resting pulse rate measurements will automatically be captured in the mobile device, while oral temperature will be captured in the eDiary ([Section 6.2.2](#)).

The Screening visit is defined as Day 1. If the visit occurs in the morning, the patient will be responsible for recording the 16:00-hour measurements at home later that day; if the visit occurs after 16:00 hours, measurements will commence at home the following morning.

6.2.2 eDiary

The eDiary will be completed by patient each day through Day 14. The following symptoms will be collected:

- Fatigue
- Chills
- Headache
- Cough (with or without sputum production)
- Myalgia
- Sore throat
- Shortness of breath
- Nasal congestion
- Diarrhea
- Nausea or vomiting

For each of these symptoms, the patient will be asked to grade them by the following scale:

- Not at all
- A little bit
- Somewhat
- Quite a bit
- Very much

The patient will also record all temperatures in the eDiary.

In the event that the patient progresses to hospitalization or is unable to complete the eDiary, family members, designated legal representatives or caregivers will be contacted, as provided by informed consent, to determine the status of the patient.

6.2.3 Telephone calls

The patient will be called each day, Day 2 through Day 14. The telephone script is provided in Appendix A of the Protocol.

After the completion of Day 14, the patient will be called weekly through Day 28. The telephone script is provided in Appendix B of the Protocol.

Based on the findings of telephone calls, an Unscheduled Visit with the Investigator or personal doctor may be scheduled (Protocol Section 8.4).

In the event that the patient progresses to hospitalization or is unable to complete the telephone calls, family members or caregivers will be contacted, as provided by informed consent, to determine the status of the patient.

6.2.4 Criteria for the Assessment of Severity of Illness in Patients with COVID-19

The criteria in Appendix C of the Protocol will be used to assess changes in the severity of COVID-19 in patients at different timepoints over the course of the trial. The final determination will be made on Day 28 in patients who are not hospitalized and Day 42 in patients who are hospitalized.

6.2.5 Additional Data Collection in Hospitalized Patients

Additional data to be collected for patients hospitalized due to COVID-19 through Day 42 to include the following:

- Date and time of hospital admission and discharge
- If transferred to ICU, date and time of ICU admission and discharge
- Requirement for oxygen (yes/no), and if yes, method of oxygenation (mask/nasal prongs, non-invasive ventilation, or high-flow oxygen; intubation and mechanical ventilation
 - If required ventilation, start date and time of ventilation, method of ventilation including whether intubated (yes/no)
- Change in ambulatory status
- Death

It is anticipated that most of this information will be obtained from the medical record. When necessary, a family member, designated legal representative or caregiver, as permitted by informed consent, will be contacted if the patient has expired or is too ill or otherwise unable to provide this information.

The rate (liters/min) of oxygen administered is to be captured as a concomitant medication. If, in the Investigator's opinion, a patient required a higher level of oxygenation, but did not receive due to resource availability, this should be documented.

Furthermore, if, in the Investigator's opinion, the patient required a higher level of care (ie, admittance to the ICU) but did not receive due to resource availability, this should be documented.

6.2.6 *Vital Status*

Vital status is to be documented at each study contact. If the patient died due to a reason other than COVID-19, the primary cause of death is to be recorded and reported as an SAE. Death due to worsening fever, cough, shortness of breath, resting SpO₂ or resting pulse rate or COVID-19 symptoms that are reported at Screening (Protocol Section 8.1.2) is not considered to be an SAE in the context of this study although cause of death will be reviewed by the DMC in real time.

6.3 **Safety Assessments**

6.3.1 *Height, Weight and Body Mass Index (BMI)*

Height (cm) and weight (kg) will be measured and recorded at Screening. BMI will be subsequently be calculated from these measurements.

6.3.2 *Physical Examination*

A cardiovascular and respiratory-focused physical examination will be performed by trained medical personnel during Screening.

6.3.3 *Screening Vital Signs*

Blood pressure and respiratory rate obtained after sitting at rest for at least 5 minutes will be recorded at Screening. The procedures for recording resting pulse rate and oral temperature are detailed in Protocol Section 8.2.1.

6.3.4 *Adverse Events*

The AE reporting period is from the start of study drug administration on Day 1 through Day 14 or until time of hospitalization. AEs will be assessed by direct observation on Day 1 and then by web-based questionnaire and patient interview during daily telephone contact through Day 14 after study drug administration and then through telephone contact thereafter until resolved, stabilized, or transitioned to the patient's main healthcare provider for follow up.

Details on the definitions, reporting, and management of AEs are provided in [Section 7](#).

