#### **8.2.5      *Additional Data Collection in Hospitalized Patients***

Additional data to be collected for patients hospitalized due to COVID-19 through Day 42 to include the following:

- Date and time of hospital admission and discharge
- If transferred to ICU, date and time of ICU admission and discharge
- Requirement for oxygen (yes/no), and if yes, method of oxygenation (mask/nasal prongs, non-invasive ventilation, or high-flow oxygen; intubation and mechanical ventilation
  - If required ventilation, start date and time of ventilation, method of ventilation including whether intubated (yes/no)
- Change in ambulatory status
- Death

It is anticipated that most of this information will be obtained from the medical record. When necessary, a family member, designated legal representative or caregiver, as permitted by informed consent, will be contacted if the patient has expired or is too ill or otherwise unable to provide this information.

The rate (liters/min) of oxygen administered is to be captured as a concomitant medication. If, in the Investigator's opinion, a patient required a higher level of oxygenation, but did not receive due to resource availability, this should be documented.

---

Furthermore, if, in the Investigator's opinion, the patient required a higher level of care (ie, admittance to the ICU) but did not receive due to resource availability, this should be documented.

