### **8.3.4 Adverse Events**

The AE reporting period is from the start of study drug administration on Day 1 through Day 14 or until time of hospitalization. AEs will be assessed by direct observation on Day 1 and then by web-based questionnaire and patient interview during daily telephone contact through Day 14 after study drug administration and then through telephone contact thereafter until resolved, stabilized, or transitioned to the patient's main healthcare provider for follow up.

Details on the definitions, reporting, and management of AEs are provided in [Section 9](#).

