### **9.2      *Reporting Responsibilities and Periods***

It is the responsibility of the Investigator to perform periodic assessment for AEs. AEs spontaneously reported by the patient or reported in response to an open question from the study personnel (eg, 'Have you had any health problems since the previous visit/you were last asked?') or revealed by observation will be recorded.

AEs and concomitant medications will be recorded from the start of study drug administration on Day 1 through 14 or until the time of hospitalization. The AE term, date of AE onset, date of AE resolution (if applicable), severity, causality, action taken for the AE, outcome and whether or not the AE was serious will be recorded.

---

AEs must be monitored until they are resolved, stabilized or transferred to the patient's main healthcare provider for follow up, are clearly determined to be due to a patient's stable or chronic condition or intercurrent illness(es), the patient is hospitalized, or follow-up is no longer possible. Data describing AEs will be recorded in the patient's medical record and as appropriate, an SAE report form. SAEs will be reported to the Sponsor as described in [Section 9.6](#).

Any SAE that the Investigator considers to be related to study drug and occurs at any time after completion of the study must be reported to the Sponsor or designee. If at the time the Investigator initially reports an SAE, the event has not resolved, the Investigator must provide a follow-up report as soon as it resolves (or upon receipt of significant information if the event is still ongoing).

Note that for the purposes of this study, hospitalization due to worsening fever, cough or shortness of breath, resting SpO2 or resting pulse rate or symptoms of COVID-19 that are reported prior to treatment ([Section 8.1.2](#)) will not be considered an SAE.

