7.2 Reporting Responsibilities and Periods

It is the responsibility of the Investigator to perform periodic assessment for AEs. AEs spontaneously reported by the patient or reported in response to an open question from the study personnel (eg, ‘Have you had any health problems since the previous visit/you were last asked?’) or revealed by observation will be recorded.

AEs and concomitant medications will be recorded from the start of study drug administration on Day 1 through 14 or until the time of hospitalization. The AE term, date of AE onset, date of AE resolution (if applicable), severity, causality, action taken for the AE, outcome and whether or not the AE was serious will be recorded.

AEs must be monitored until they are resolved or, stabilized or transferred to the patient’s main healthcare provider for follow up., are clearly determined to be due to a patient’s stable or chronic condition or intercurrent illness(es), the patient is hospitalized or follow-up is no longer possible. Data describing AEs will be recorded in the patient’s medical record and as appropriate, an SAE report form. SAEs will be reported to the Sponsor as described in Protocol Section 9.6.

Any SAE that the Investigator considers to be related to study drug and occurs at any time after completion of the study must be reported to the Sponsor or designee. If at the time the Investigator initially reports an SAE, the event has not resolved, the Investigator must provide a follow-up report as soon as it resolves (or upon receipt of significant information if the event is still ongoing).

Note that for the purposes of this study, hospitalization due to worsening fever, cough or shortness of breath, resting SpO₂ or resting pulse rate or symptoms of COVID-19 that are reported at Baseline will not be considered an SAE.

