9.10.1 Adverse Events

All AEs recorded on the AE eCRF during the study will be coded to SOC and PT using the most current version of MedDRA, currently MedDRA 20.1.

A treatment-emergent AE (TEAE) is defined as an AE that was not present prior to treatment with IP, but appeared following treatment or was present at treatment initiation but worsened during treatment. An AE that was present at treatment initiation but resolved and then reappeared while the patient was on treatment is a TEAE (regardless of the intensity of the AE when the treatment was initiated). Programmatically, an AE will be classified as a TEAE if the start date and time occurs on or after the start date and time of first IP dosing.

All reported AEs will be listed, but only TEAEs will be summarized.

The overall incidence of TEAEs (number and percentage of patients, 95% CI) as well as the number of events will be summarized by treatment group, intensity as assessed by the latest version of National Cancer Institute's Common Terminology Criteria for AEs, SAE, related TEAE, TEAEs leading to study or investigational product discontinuation, and SAEs resulting in death.

The number (percentage, 95% CI) of patients with AEs from Day 1 to Day 42 (including SAEs) will be summarized for each MedDRA system organ class and PT and by treatment group. The number (percentage) of patients with SAEs from Day 1 to Day 210 will be summarized in a similar fashion. The number (percentage, 95% CI) of patients with AEs by severity and by relationship to IP will also be summarized.

The TEAEs will be summarized and tabulated at both the patient (n [%] of patients) and event (number of events) level for each treatment group and overall as follows:

- SOC and PT
- SOC, PT, and maximum reported severity
- SOC, PT, and maximum relationship to investigational product

Subjects with SAEs will also be summarized by SOC and PT for each treatment group and overall.

For the incidence at the patient level by SOC and PT, if a patient experiences more than 1 event within the same SOC and PT, only one occurrence will be included in the incidence.

For the incidence at the patient level by SOC, PT, and severity, if a patient experiences more than 1 event within the same SOC and PT, only the most severe occurrence will be included in the incidence.

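### AE recording stops at hospitalization, a primary-endpoint event, so AE observation time depends on outcome and does not match the SAP's reporting windows

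*SAP*

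**What the plan says.** Protocol 8.3.4 states the rule: "The AE reporting period is from the start of study drug administration on Day 1 through Day 14 or until time of hospitalization". SAP 6.3.4 repeats it ("through Day 14 or until time of hospitalization"). Protocol 9.2 says that AEs and concomitant medications "will be recorded from the start of study drug administration on Day 1 through 14 or until the time of hospitalization", and SAP 7.2 does the same ("through 14 or until the time of hospitalization"). The same two sections also end the monitoring of AEs that are already open once "the patient is hospitalized or follow-up is no longer possible" (SAP wording).

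After admission, a separate dataset takes over. Protocol 8.2.5 introduces it as "Additional data to be collected for patients hospitalized due to COVID-19 through Day 42 to include the following". The list covers admission and discharge, ICU stay, oxygen, ventilation, ambulatory status and death. AEs are not on it.

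On the analysis side, SAP 9.10.1 tabulates numbers and percentages of patients with AEs from Day 1 to Day 42, and of "patients with SAEs from Day 1 to Day 210". It gives no adjustment for time at risk and does not treat admission as a competing event.

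**The concern.** Hospitalization is part of the primary endpoint (Protocol 3.1, SAP 3.1). A rule that closes AE recording at admission therefore makes the length of safety observation depend on treatment outcome. If one arm has more admissions, its patients are watched for fewer days, and a crude percentage will tend to make that arm look safer.

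Three things are at stake. First, safety and tolerability is the primary safety objective. Second, one halt criterion in Protocol 7.2, lettered (c) in the Study Summary, counts related Grade 3 AEs; a non-serious Grade 3 event that starts in hospital is outside the recording period. Third, under Protocol 4.1 the review between cohorts can start once each patient has either finished 14 days at home or been admitted, so for admitted patients AE recording is already closed when the DMC considers moving to a higher-risk cohort.

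The Day 42 and Day 210 labels make this harder to see, because they suggest a uniform window that was never collected.

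**Working it through.** The documents give no expected AE rate, hospitalization rate or admission day, so there is no planned figure to reproduce. The steps below use the documents' arm sizes and halt thresholds; everything else is marked as assumed.

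**1. Collection and reporting windows compared**

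| Item | Window | Source |
|---|---|---|
| New AEs | Day 1 to Day 14 or admission | Protocol 8.3.4, 9.2; SAP 6.3.4, 7.2 |
| Open AEs | Until resolved, stabilized or handed over, but also ended by admission | Protocol 9.2; SAP 7.2 |
| Last contact | Day 28, or Day 42 if still hospitalized | Protocol 4.1 |
| AE table | Day 1 to Day 42 | SAP 9.10.1 |
| SAE table | Day 1 to Day 210 | SAP 9.10.1 |

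The AE table label runs past the recording period for every patient, and the SAE label runs past the end of study follow-up.

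**2. Most admissions in one arm without exceeding a halt threshold**

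Arm sizes are 10, 14 and 24; thresholds are 15%, 20% and 25%, each to be exceeded (Protocol 4.1 and 7.2). Rates are taken on the full cohort arm.

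- Cohort 1: 1/10 = 10%; 2/10 = 20% exceeds 15%.
- Cohort 2: 2/14 = 14.3%; 3/14 = 21.4% exceeds 20%.
- Cohort 3: 6/24 = 25% does not exceed 25%.
- Total: 1 + 2 + 6 = 9 of 48 (18.8%).

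**3. Share of the 14-day AE window lost in that arm**

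Full window: 48 × 14 = 672 patient-days. Loss = 9 × (14 − h), where h is the admission day (assumed).

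- h = 6: 9 × 8 = 72; 72/672 = 10.7%.
- h = 10: 9 × 4 = 36; 36/672 = 5.4%.
- h = 4: 9 × 10 = 90; 90/672 = 13.4%.

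**4. Effect on the between-arm comparison**

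Assume a constant AE hazard, the same in both arms and in hospital, giving 14-day risk R. A patient admitted on day h has recorded risk F = 1 − (1 − R)^(h/14). The true difference is zero. The recorded difference is −(pA − pB) × (R − F), where pA and pB are the admitted proportions.

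With R = 40% and h = 6: F = 1 − 0.6^(6/14) = 19.7%. For 9 against 3 admissions, the difference is −(6/48) × (40.0 − 19.7) = −2.5 points, in favour of the arm with more admissions. Over R = 20% to 60% and h = 3 to 7 it runs from −1.2 to −5.3 points; for 9 against 0 admissions, from −1.8 to −7.9.

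If the in-hospital hazard is three times higher (assumed), the bias for 9 against 3 is −3.2 to −9.1 points, and the recorded difference has the opposite sign to the true one in every scenario run.

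If pA = pB, with the same timing and in-hospital hazards in both arms, the bias is zero.

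**The case against.** A reader might infer that severe in-hospital events are simply not captured. The documents do not support that. Protocol 9.6.2 requires SAEs to be reported within 24 hours regardless of relationship and sets no end at admission. The SAE definition in Protocol 9.1.3 includes prolongation of an existing hospitalization, which can only happen after admission. Deaths from causes other than COVID-19 are SAEs (Protocol 8.2.6). For COVID-19 admissions, ICU stay, ventilation and death are collected to Day 42. The DMC sees hospitalizations and deaths in real time, and two further halt criteria act directly on hospitalization and ventilation. What remains is that SAE collection after admission is implied rather than stated, and that non-serious in-hospital AEs are outside the period.

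A reader might also apply the 25% threshold to a whole arm and put the loss at 14% (Day 6) to 18% (Day 4). That threshold belongs to Cohort 3 only. Across the three cohorts the ceiling without exceeding any threshold is 9 of 48. More admissions are possible, but only if dosing resumes after a DMC review.

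It is also fair to say that the trial is exploratory, that its AE summaries are descriptive, and that worsening COVID-19 was deliberately routed to efficacy. This lowers the stakes, but it does not justify percentages under a window label that differs from what was observed.

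**Conclusion.** The point stands in this form: AE observation time depends on the outcome, the SAP's summary windows do not match collection, and the SAE window for admitted patients is unclear. It should be corrected, because following the plan as written produces the imbalance.

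The size is moderate. At the ceiling of 9 of 48 admissions, one arm loses 10.7% of its 14-day AE window with admission on Day 6, and 5.4% to 13.4% for Day 10 to Day 4. The admission day is assumed; the ceiling follows from the halt thresholds and is not an expected rate. Lost days in one arm do not by themselves bias the comparison. Bias needs a difference in admission rates, timing or in-hospital hazards. With 9 against 3 admissions and equal hazards, it is a few percentage points under the assumed AE risks.

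**What to change.** - In Protocol 8.3.4 and 9.2 and SAP 6.3.4 and 7.2, delete the clause that ends AE recording at hospitalization, so that AEs are recorded through Day 14 for every patient, from the medical record after admission. Remove admission as an end to monitoring of open AEs in 9.2 and 7.2 to match. Apart from death and withdrawal, each arm then contributes up to 672 patient-days and the truncation bias above disappears.
- State one SAE window for all patients regardless of hospitalization, for example to Day 28, the last scheduled contact. Extending collection for admitted patients alone would give them a longer severe-event window than patients at home and reverse the imbalance.
- In SAP 9.10.1, align the Day 42 and Day 210 labels with these windows, and report AE observation time and patient-day rates by arm beside the crude percentages. Patient-day rates are a supplement: on their own they remove the bias only if the AE hazard is the same in and out of hospital.
- Separately, reconcile the concomitant-medication period in Protocol 9.2 (Day 14 or admission) with 6.7 (30 days after dosing) and 6.7.1 (all in-hospital medication). Antipyretic and bronchodilator use is a safety endpoint.

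The cost is protocol and SAP wording, plus abstraction, grading and causality assessment for the few admitted patients. Protocol 8.2.5 already expects most in-hospital data to come from the medical record, but its list is short, so this is additional work. There will also be more expected in-hospital events to describe.
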